 - This includes all hospital bed days during emergency admissions in the 28 days from first COVID-19 positive test. If the patient is still in hospital on day 28 then bed days will be truncated on day 28. Except for same-day admissions, bed days are counted as number of nights in hospital. Thus, an admission on day one and discharge on day three would equate to two bed days. Same day admission-discharges will be treated as a half-day.
 - We will evaluate total hospital bed days as opposed to average length of stay (LOS) in order to better capture the hospital resources required to care for a patient. For example, a patient's single stay of 3 days or two stays of 3 days would both result in an average LOS of 3 days, whereas the total number of hospital bed days would be 3 and 6 days, respectively.

- Total hospital bed days in critical care
 - This includes all bed days in critical care (see definition above) in the 28 days from first COVID-positive test. If the patient is still in a critical care bed on day 28 then bed days will be truncated on day 28. Same-day admission-discharges will be treated as a half-day.
- Death (binary yes/no)
 - This will include deaths recorded within the 28-day follow-up period. This is consistent with the definition of COVID-19 deaths used for reporting by Public Health England.

Hypothesised outcomes

The primary outcomes for this study are whether a patient was allocated a critical care bed, total hospital bed days in critical care, and death. The CO@h programme's logic model hypothesises that early escalation of deteriorating patients will result in fewer patients needing critical care, less time spent in critical care, and fewer deaths. It may be, however, that a decrease in mortality results in longer stays in hospital, on average, due to more patients surviving while still becoming severely ill.

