Where relevant, we will make use of the Benjamini-Hochberg procedure²⁸ to adjust for the increase in the false discovery rate (type 1 errors) due to multiple testing.²³

Descriptive analyses of patient flow

For context, we will create a flow diagram based on the CONSORT standard²⁹ of how patients move between receiving a COVID-19 positive test, are onboarded and use hospital services. This will help visualise some of the implicit decisions that we make, for example by showing the number (and percentage) of patients that were first enrolled following A&E. We will also check and document the number (and percentage) of patients who were onboarded without a COVID-19 positive test, and therefore excluded from our analysis.

We will also use the onboarding data to understand the enrolled population: the number of patients who are enrolled due to age, CEV status, both or neither. Likewise, we will consider these categories in those patients who were not enrolled. As long as these patients are flagged as CEV in the GDPDR data, we will be able to identify these patients.

Subgroup analyses

As care home residents will have access to support to use the pulse oximeters and record measurements correctly, care home residency may act as an effect modifier. However, as it is possible that many care home residents below 65 years of age will also be eligible for CO@h (eg because of learning disabilities, according to the SOP) it will probably not be possible to do a subgroup analysis on care home residents using the RDD method and we may exclude these patients from the study cohort. If they are not excluded, we may still run an RDD in the subgroup of patients not in care homes, which would potentially allow for an analysis with a sharper discontinuity at age 65.

Given the inequalities that COVID-19 has exposed, it is important to understand whether technologies such as the use of remote pulse oximeters are helping the communities worst affected by the pandemic. If the study is sufficiently powered, we will estimate the intervention effect in patients who live in the most socio-economically deprived areas. We could look at either the most deprived IMD quintile or the aggregate of the two most deprived IMD quintiles. We may also estimate the intervention effect in patients of different ethnic groups

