(White, Black, Asian, Mixed and Other). Depending on the achieved power, this may be limited to a broader group of ethnicities (eg 'ethnicities other than White'). Once we know more about the quality of onboarding data and numbers of patients enrolled, we will make an assessment as to what is possible in terms of subgroup analyses.

Reporting

Our reporting of the study will aim to meet the requirements of the STROBE checklist for the reporting of cohort studies.³⁰

Power calculation

A set of power calculations for binary outcomes (eg ICU: yes/no) are shown in Table 1, below.

Table 1: Total sample sizes resulting from power calculations

| Total sample sizes (N) | | Relative risk in treated group | | |
|---------------------------|-------|--------------------------------|--------|---------|
| | | 50% | 75% | 90% |
| Baseline risk | 10.0% | 870 | 4,010 | 26,990 |
| | 5.0% | 1,812 | 8,404 | 56,816 |
| | 4.0% | 2,282 | 10,602 | 71,730 |
| | 3.0% | 3,068 | 14,266 | 96,584 |
| | 2.0% | 4,638 | 21,590 | 146,294 |
| | 1.0% | 9,346 | 43,568 | 295,422 |
| | 0.5% | 18,766 | 87,522 | 593,680 |

Note: equal sized treatment and control groups of N/2; full compliance assumed, two-sided tests; power 80%; alpha 5%.

The power calculations are based on standard large sample approximations. Power calculations using Fisher-based randomisation inference produce similar results to those based on large sample approximations. For example, assuming two equally sized groups, a two-sided test at the 5% significance level, and an outcome of 2% in the control group and 1.5% in the treated group, a sample size of around 22,000 (11,000 in each group) would be required to achieve a power of 80% (based on a simulation with 10,000 draws).

These power calculations demonstrate that relatively large samples will be required to identify treatment effects of CO@h on the primary outcomes, particularly for infrequent outcomes such as ICU admittance. For reference, the mixed-methods study of pilots of remote home monitoring models in England found that for the pre-hospital model of CO@h, approximately 8% of onboarded patients attended A&E, 5% were admitted to hospital in an emergency, 0.2% were admitted to ICU and 1% died.¹

Strengths and limitations

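### The subgroup plan estimates effects only within deprived and ethnic groups and never against the remaining patients, so it cannot show whether CO@h works differently in the communities worst affected

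*SAP*

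**What the plan says.** Under Subgroup analyses, the SAP gives inequality as the motive and says that, provided the study has enough power, "we will estimate the intervention effect in patients who live in the most socio-economically deprived areas". The definition of deprived is left open: "We could look at either the most deprived IMD quintile or the aggregate of the two most deprived IMD quintiles". On ethnicity it adds "We may also estimate the intervention effect in patients of different ethnic groups", naming five groups, and then "Depending on the achieved power, this may be limited to a broader group of ethnicities". What is feasible will be assessed once the quality of the onboarding data and the number enrolled are known.

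The section plans no contrast between a subgroup and the rest of the cohort. It does recognise effect modification, but only for care home residency. It does not say which outcomes the subgroup analyses cover, gives no criterion for enough power, and does not call the results exploratory.

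Three provisions elsewhere bear on this:
- The end of Sensitivity analyses applies Benjamini-Hochberg where relevant, without defining the family of tests.
- Study design promises that decisions made after the SAP is final will be documented and justified in an addendum. It does not say that this must happen before outcomes are seen, and it allows interim analyses on incomplete data.
- Main analysis provides confidence intervals for treatment effects.

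**The concern.** An inequality question is comparative: is the benefit in deprived or minority ethnic patients smaller than, equal to or larger than the benefit elsewhere? An estimate from one group alone does not answer it. Readers will set the group's result beside the overall result, or beside another group's, and compare significance. That comparison misleads. A smaller group can miss significance only because it is smaller, while the larger remainder reaches it with the same effect. At stake is a policy-sensitive statement that CO@h does not help deprived or minority ethnic patients, made when the benefit is the same for everyone. The primary analysis is not affected.

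**Working it through.** **Inputs from the SAP.** Table 1 and its note (Power calculation): two-sided 5%, 80% power, equal groups, full compliance. Worked example: "an outcome of 2% in the control group and 1.5% in the treated group". Table 1 row: "2.0% | 4,638 | 21,590 | 146,294" for relative risks of 50%, 75% and 90%. Primary outcomes (Hypothesised outcomes), three in number: "The primary outcomes for this study are whether a patient was allocated a critical care bed, total hospital bed days in critical care, and death".

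**Assumptions, not in the SAP.** The subgroup holds a share f of the patients in the window: 20% for one quintile or 40% for two. Risks, effect and above/below-65 split are the same in subgroup and complement.

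**1. Reproduce the SAP's figure.** With p1 = 0.02, p2 = 0.015 and mean 0.0175, the pooled-variance formula gives

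n per group = [1.960 × √(2 × 0.0175 × 0.9825) + 0.842 × √(0.02 × 0.98 + 0.015 × 0.985)]² / 0.005² = 10,795,

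so the total is 21,590, as stated. All 21 cells of Table 1 reproduce in the same way.

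**2. Power within a subgroup, same benefit in everyone.** At 80% power the expected z overall is 1.960 + 0.842 = 2.802. In a share f it is 2.802 × √f, and power is about Φ(2.802 × √f − 1.960).
- f = 20%: z = 1.253, power 24.0%. Complement (80%): z = 2.506, power 70.7%.
- f = 40%: z = 1.772, power 42.5%. Complement (60%): z = 2.170, power 58.3%.

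**3. Opposite verdicts.** Subgroup and complement share no patients, so their results are treated as independent.
- f = 20%: subgroup misses and rest significant, 0.760 × 0.707 = 53.8%; the reverse, 0.240 × 0.293 = 7.0%; total 60.8%.
- f = 40%: 0.575 × 0.583 = 33.5%; the reverse, 0.425 × 0.417 = 17.7%; total 51.2%.

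(Products are taken before rounding.)

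**4. If the power condition means 80% power in the subgroup itself.**
- f = 20%: total N = 21,590 / 0.2 = 107,950. The complement has over 99.9% power, and the subgroup still misses an identical benefit 20% of the time.
- f = 40%: total N = 21,590 / 0.4 = 53,975. The complement has 92.9% power. The pattern of subgroup missing and rest significant occurs in 0.20 × 0.929 = 18.6% of studies.

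**5. Precision of the missing contrast.** The variance of subgroup minus complement is the overall variance × 1/[f(1 − f)]: 6.25 times for f = 20% and 4.17 times for f = 40%. For a true difference as large as the overall effect (0.5 percentage points) at N = 21,590, the expected z is 2.802 × √[f(1 − f)].
- f = 20%: 1.121, power 20.1%.
- f = 40%: 1.373, power 27.8%.

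**The case against.** The best defence has four parts.

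*The question is whether deprived communities are helped, and a within-group estimate with an interval answers that.* This is partly right. The SAP says estimate, and nowhere says that significance will be compared between groups. But the stated motive is inequality, and without a planned contrast the only comparison a reader can make is the misleading one.

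*The analyses run only if powered.* This stands as a limit on step 3: the 61% and 51% apply if 80% power overall is taken as enough. The condition attaches to the study and has no criterion. Under the stricter reading in step 4 the problem shrinks but does not vanish.

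*The open choices depend on numbers, not results.* This stands as far as it goes. A cut chosen on sample size does not inflate error. What remains is that nothing dates the choice before outcomes are seen.

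*The proposed contrast has low power.* True, and it is a reason to label the results exploratory. An interval shows the imprecision that separate verdicts conceal.

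A reader might go further and infer that chance findings are uncontrolled, citing about 60% for at least one false positive from six subgroups on three outcomes (1 − 0.95^18), or about 8.3% instead of 5% for the better of two deprivation cuts. The document does not support this. The first figure assumes independent, unadjusted tests, yet the groups overlap, the outcomes are related and the SAP names Benjamini-Hochberg. If applied across these tests, that procedure would hold the chance of any false positive at about 5% when no effect exists, for independent or positively dependent tests. The second figure assumes that both cuts are run and the better one reported, whereas the text offers one or the other. Nor does the SAP say that subgroups will be run on every outcome. Benjamini-Hochberg has no defined family here, and it does not address false differences between groups.

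**Conclusion.** The point holds as a weakness of method, not as a claim of uncontrolled false positives. As written, the subgroup section cannot show whether CO@h works differently in deprived or minority ethnic patients. With an identical benefit and 80% power overall, a 20% (40%) subgroup is significant about 24% (43%) of the time and disagrees with the remainder in about 61% (51%) of studies. With 80% power in the subgroup itself, it still misses an identical benefit 20% of the time. These figures rest on the assumed shares, equal risks across groups and the SAP's assumption of full compliance; non-compliance would lower subgroup power further at a given N. The open cut and the missing exploratory label would be minor on their own. They matter because no contrast anchors the interpretation. The change should be made, but it does not touch the primary analysis.

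**What to change.** Before outcome data are seen, including for any interim analysis, record in the SAP or its addendum:

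- one deprivation cut and one ethnic grouping, chosen on patient numbers only;
- that subgroup analyses cover the three primary outcomes;
- that each subgroup estimate is reported beside the estimate for its complement, with the difference between them and a 95% confidence interval, all from the same age window;
- that these results are exploratory, and that any statement about differing benefit rests on the difference and its interval, not on significance within a group.

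The cost is a few sentences and one extra contrast per subgroup and outcome, from data already to be held. The downside is a wide interval: at N = 21,590, power is about 20% to 28% for a difference as large as the overall effect. A significant result in one group could also no longer be presented as evidence that the group benefits more or less than others.
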